8.5. Data and Safety Monitoring Plan

The proposed study will conform to rigorous standard monitoring procedures, standardized reporting of adverse events (Adverse Event Report Forms are completed by study coordinators and sent immediately to the investigators), and regular review of the study by a Data and Safety Monitoring Board (DSMB). The PI has primary responsibility for the overall conduct of the study, including the safety of human subjects. The PI will ensure appropriate (1) conduct of the informed consent process (e.g. that informed consent is obtained before proceeding with study procedures); (2) enrollment of study subjects; (3) collection and analysis of data; (4) implementation of study procedures to ensure consistent monitoring of subjects for possible adverse events; (5) review of adverse events and reporting to the DSMB and the IRBs; and (6) maintenance of the privacy and confidentiality of study subjects. The PI maintains ultimate

responsibility for the project and for the safety of study participants. The PI will be in contact with the research team on a regular basis to review the progress of the study and address any human subject issues that occur. These discussions may involve adverse event prevention measures, recruiting of appropriate study subjects, research staff training on protection of human subjects, as well as occurrence of adverse events, unexpected incidents, or protocol problems.

8.5.1. Data and Safety Monitoring Board

A DSMB will be established by the study team in cooperation with the sponsor to assess at intervals the progress of a clinical trial, safety data, and critical efficacy variables and recommend to the sponsor whether to continue, modify or terminate a trial. The DSMB will have written operating procedures and maintain records of all its meetings, including interim results; these will be available for review when the trial is complete. The DSMB will be a separate entity from the US and host-country Institutional Review Boards (IRBs). The independence of the DSMB is intended to control the sharing of important comparative information and to protect the integrity of the clinical trial from adverse impact resulting from access to trial information. DSMB members will not participate in the study as investigators and will not have conflicts of interest regarding the study or the investigational product. The composition of the DSMB will include at minimum:

DSMB Chair, having experience and expertise in clinical trials Scientist with expertise in malaria and malaria inpregnancy Biostatistician with expertise in clinical trials.

A member of the sponsor, NICHD, will be invited to attend and thus have access to unblinded information, and control of dissemination of interim trial results within the sponsor organization. The DSMB will meet at least annually to review progress of the clinical trial and safety data.

The DSMB will review the study for progress and safety. The PI will provide information that will allow the DSMB to review and assess the following:

- The research protocol, informed consent documents and plans for data safety and monitoring;
- Periodic assessments of data quality and timeliness, participant recruitment, accrual and retention, participant risk versus benefit, and other factors that can affect study outcome;
- Factors external to the study when relevant information, such as scientific or

therapeutic developments, may have an impact on the safety of the participants or the ethics of the trial;

- Study performance to make recommendations and assist in the resolution of problems;
- The safety of the study participants;
- The safety and scientific progress of the trial;
- The continuation, termination or other modifications of the trial based on the observed beneficial or adverse effects of the treatment under study;
- The confidentiality of the data and the results of monitoring; and
- Any problems with study conduct, enrollment, sample size and/or data collection.

The first meeting of the DSMB will take place prior to the initiation of the study to discuss the protocol and the Data Safety Monitoring Plan. Meetings of the DSMB shall be held according to the plan outlined above. Meetings shall be closed to the public because discussions may address confidential patient data. Meetings may be convened as conference calls as well as in person. An emergency meeting of the Board may be called at any time should questions of patient safety arise. The DSMB may request the presence of study investigators at such meetings.

The study PI will distribute study information to the DSMB at least 10 days prior to a scheduled meeting. The DSMB may request additions and other modifications to this information on a one-time or continuing basis. This information will consist of two parts: (1) information on study progress such as accrual, baseline characteristics, and other general information on study status and (2) any confidential data on study outcomes, including safety data. A formal report from the DSMB should be supplied to the PI within 6 weeks of each meeting. Each report should conclude with a recommendation to continue or to terminate the study. This recommendation should be made by formal majority vote. A recommendation to terminate the study should be transmitted to the PI, IRBs and NIH as rapidly as possible, by immediate telephone and fax if sufficiently urgent. In the event of a split vote in favor of continuation, a minority report should be contained within the regular DSMB report.

8.5.2. Interim safety analysis

Over the course of the trial, we will perform one interim safety analysis in addition to a final safety analysis for a total of two sequential evaluations of study safety for the pregnant women. The interim safety analysis will be performed when ½ of the study subjects have given birth. A standardized test statistic will be calculated for the incident rate ratio of significant adverse

events (grade 3/4 & SAEs). If this statistic exceeds the nominal critical value calculated using the error spending function (Table 5), then a statistically significant result will have been achieved at the time of that analysis. In that event, the sponsor will be notified and a report submitted for review by the Data Safety Monitoring Board (DSMB). The study team will present the results of the interim safety analyses to the DSMB, which will review the data and recommend a course of action.

Number of Evaluable Subjects Accrued	Test St	atistic	Alpha	Cumulative	
or % of Total Accrual	Lower Bound	Upper Bound	Аірпа	Alpha	
N=391 or 50% of accrual	-2.51	2.51	0.00601	0.01210	
N=782 or 100% of accrual	-1.99	1.99	0.02313	0.05000	

Table 5. Schedule of interim safet	y analysis and boundaries to monitor study	outcome
Tuble 5. Selledule of Internit Suret		outcome

This analysis assumes α=0.05 (two-sided test), O'Brien-Fleming boundaries (DeMets errorspending function) and 782 trial participants. We will utilize Programs for Computing Group Sequential Boundaries Using the Lan-DeMets Method.

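### Table 5's interim safety boundaries are not O'Brien-Fleming values for one look at 50%; they match looks 2 and 3 of a three-look schedule, and used as labelled they give overall alpha 0.0526

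*Combined protocol and SAP*

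**What the plan says.** Section 8.5.2 fixes the number of looks: "we will perform one interim safety analysis in addition to a final safety analysis for a total of two sequential evaluations". It fixes the timing: "The interim safety analysis will be performed when ½ of the study subjects have given birth". It names the method: "This analysis assumes α=0.05 (two-sided test), O'Brien-Fleming boundaries (DeMets errorspending function) and 782 trial participants". The software is to be the Lan-DeMets group sequential programs. The statistic is a standardised test of the incidence rate ratio for grade 3/4 adverse events and SAEs.

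Table 5 then gives two rows (lower bound, upper bound, alpha, cumulative alpha): "N=391 or 50% of accrual -2.51 2.51 0.00601 0.01210" and "N=782 or 100% of accrual -1.99 1.99 0.02313 0.05000".

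If the statistic exceeds the tabulated value, the result counts as statistically significant at that analysis, the sponsor is notified, and a report goes to the DSMB. Section 8.5.3 leaves any decision to stop to the DSMB and gives no other numerical threshold.

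**The concern.** O'Brien-Fleming-type spending releases very little alpha halfway through a trial, and a bound of 2.51 at 50% is too low for it. If the rows belong to another schedule, the protocol contains two incompatible rules: the one in the text and the one in the table. A statistician running the named program at 50% would get a bound near 2.96. The DSMB could then face an interim |Z| between 2.51 and 2.96 that is significant by the table and not by the method. That dispute would arise with unblinded data on the table. The cumulative alphas printed in Table 5 would also be untrue for the looks they are attached to.

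**Working it through.** **Inputs** (all from section 8.5.2): two-sided alpha 0.05; O'Brien-Fleming-type Lan-DeMets spending; two looks; interim labelled 50%, so t = 0.5, then t = 1.

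**1. What the alpha column means.** The upper-tail probability is 0.00604 at 2.51 and 0.02330 at 1.99. The printed 0.00601 and 0.02313 correspond to 2.5116 and 1.9930, which round to the printed bounds. The column is therefore the nominal one-sided alpha, and the cumulative column is two-sided.

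**2. Internal check on row 1.** At a first look, cumulative two-sided alpha is exactly twice the nominal one-sided alpha: 2 × 0.00601 = 0.01202. The table prints 0.01210. Rounding of 0.00601 (0.006005 to 0.006015) allows only 0.01201 to 0.01203. Some alpha had already been spent before this row, yet the plan has no earlier look.

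**3. Reproducing the printed figures.** Spend 0.025 in each tail: α*(t) = 4[1 − Φ(z₀.₉₈₇₅/√t)], with z₀.₉₈₇₅ = 2.2414.

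- t = 1/3: 2.2414/0.5774 = 3.882, α* = 0.00021
- t = 2/3: 2.2414/0.8165 = 2.745, α* = 0.01210
- t = 1: α* = 0.05000

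Bounds solved by recursive integration of the joint normal distribution:

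| Schedule | Look | Bound | One-sided alpha | Cumulative alpha |
|---|---|---|---|---|
| 1/3, 2/3, 1 | 1 | 3.710 | 0.00010 | 0.00021 |
| | 2 | 2.511 | 0.00601 | 0.01210 |
| | 3 | 1.993 | 0.02313 | 0.05000 |
| 2/3, 1 | 1 | 2.509 | 0.00605 | 0.01210 |
| | 2 | 1.993 | 0.02314 | 0.05000 |
| **Table 5** | 50% | 2.51 | 0.00601 | 0.01210 |
| | 100% | 1.99 | 0.02313 | 0.05000 |

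Looks 2 and 3 of the three-look schedule match every printed figure. The two-look (2/3, 1) schedule misses in the nominal alphas. The missing first row (0.00021) also explains the mismatch in step 2.

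**4. The stated design.** At t = 0.5: 2.2414/0.7071 = 3.170 and α* = 0.00305. The first bound solves 2[1 − Φ(c₁)] = 0.00305, so c₁ = 2.963 (0.00153 per side). The final bound solves P(|Z₁| < 2.963, |Z₂| < c₂) = 0.95 with correlation √0.5 = 0.7071, so c₂ = 1.969 (0.02450 per side, cumulative 0.05000).

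**5. Other conventions at (0.5, 1).** Spending 0.05 directly as two-sided gives 2.772 and 1.979 (interim alpha 0.00557). Classical O'Brien-Fleming gives 2.797 and 1.977 (0.00517). Pocock gives 2.178 at both looks. None gives 2.51.

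**6. Effect of the printed bounds at (0.5, 1).**

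- False interim crossing: 2[1 − Φ(2.51)] = 0.01207, or 0.01210 as printed. Ratio to the intended spend: 0.01210/0.00305 = 3.97.
- Overall: 1 − P(|Z₁| < 2.51, |Z₂| < 1.99) = 0.0526. With the unrounded bounds 2.5116 and 1.9930 it is 0.0522.
- If 2.51 is kept at 50%, the final bound that restores 0.05 is 2.016.

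**The case against.** The strongest objection is that t = 0.5 is itself doubtful. Spending runs on information, and for a rate ratio this follows events and person-time. When half the women have delivered, those still pregnant have already contributed follow-up, so the true fraction probably exceeds 0.5. The documents give no accrual period. Assuming uniform accrual over 40 to 130 weeks, a constant event rate, 20 to 26 weeks on study before delivery and 6 weeks after it, the fraction is about 0.55 to 0.74. The effect of the printed bounds then changes as follows:

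| t | Interim bound by the stated method | Interim alpha, printed 0.01210 vs method | Overall alpha with 2.51 and 1.99 |
|---|---|---|---|
| 0.50 | 2.963 | 4.0-fold | 0.0526 |
| 0.55 | 2.806 | 2.4-fold | 0.0519 |
| 0.60 | 2.669 | 1.6-fold | 0.0512 |
| 0.65 | 2.547 | 1.1-fold | 0.0505 |
| 0.70 | 2.438 | 0.8-fold | 0.0498 |

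The four-fold figure also depends on the spending convention. Under direct two-sided spending it is 0.01210/0.00557 = 2.2. The overall excess is at most 0.0026, a crossing prompts review rather than stopping, and a sensitive safety trigger errs towards caution.

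All of this limits the practical impact. It does not rescue the table. Table 5 labels its own look 50%, and the plan defines no other information scale. The printed 0.01210 fits the spending function, in the form that reproduces the table, only at t = 0.667. The contradiction within row 1 holds at any fraction and under any convention.

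**Conclusion.** The concern holds: Table 5 is wrong as written. Under the plan's own label of 50%, the interim bound should be 2.963 where 2.51 is printed, and the final bound 1.969 where 1.99 is printed. False interim crossings rise from 0.31% to 1.21%, and overall two-sided alpha is 0.0526 instead of 0.0500. These sizes assume t = 0.5 and 0.025 spent in each tail, which is the convention that reproduces the printed digits. They shrink if the true information fraction is higher.

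That the rows come from a three-look run is an inference from an exact numerical match; the documents do not say so. The error concerns the safety monitoring rule only and leaves the alpha of the primary efficacy test untouched. It still has to be corrected, because it is the plan's only numerical monitoring threshold and it disagrees with the method stated beside it.

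**What to change.** Settle the rule before any unblinded interim comparison is made. Two consistent choices:

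1. **Keep the stated method.** Replace the rows with: 50%, ±2.963, alpha 0.00153 per side, cumulative 0.00305; 100%, ±1.969, alpha 0.02450 per side, cumulative 0.05000.
2. **Keep the more sensitive ±2.51 trigger at 50%.** Stop describing it as O'Brien-Fleming, print 0.00604 per side and cumulative 0.01207 for that look, and use ±2.016 at the final look so that cumulative alpha is 0.05.

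With either choice, label the alpha column as one-sided nominal and state how information is measured (for example, observed events or person-time as a fraction of the planned total). Under choice 1, say that the bounds will be recomputed at the observed fraction with the Lan-DeMets program already named. Under choice 2, say that the final bound will be recomputed in the same way.

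The cost is a handful of table entries and one or two sentences in section 8.5.2. Nothing changes for participants, visits or data collection.

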8.5.3. Stopping rules

The DSMB will determine whether to stop the study for early evidence of intervention safety problems after a thorough review of interim data. Interim reports will provide cumulative enrollment figures and cumulative adverse birth outcomes, serious adverse events (classified according to grade), sorted by study arm. Brief clinical descriptions of key events will also be provided. The PI will be responsible for immediately reporting to the funding agency any temporary or permanent suspension of the project and the reason for the suspension.

9. DATA COLLECTION AND MONITORING

9.5. Record Keeping

All clinical data will be recorded onto standardized case record forms (CRFs) by study clinicians. Blood smear results will be recorded in a laboratory record book by the study laboratory technologists and then transferred to the case record forms by study coordinators, who will review the case record forms frequently for completeness and accuracy. Other laboratory data (CBC, ALT measurements) will be entered into the CRFs and hard copies of the original results will be stored in a file. Data will be entered directly from CRFs into a computerized database or transferred from the CRFs onto standardized data extraction forms and then into a computerized database. All computerized data will be double entered to verify accuracy of entry. Electronic data including all study databases and supporting electronic documentation will be archived to large-scale digital tape on a daily basis. On a monthly basis, a complete backup tape will be transported off-site to the Kampala Data Management Center for rotating secure storage.

9.6. Data Quality Assurance and Monitoring

In order to insure data quality, the study Data Manager will perform a quarterly data quality audit. For this audit a 1% random sample of study forms entered into the data management system from the previous 2 weeks will be selected and compared for accuracy with the original case-report forms and source documents. In addition the study Data Manager will perform monthly reviews of the 100% double data entry data verification logs and the data management system audit trail log to identify potential data quality issues. The data will be owned by the Makerere University-University of California, San Francisco Research Collaboration.

10. HUMAN SUBJECTS

10.5. Subject Selection Criteria

Study subjects will be HIV-uninfected pregnant women and the children born to them who meet our selection criteria and provide informed consent. We plan to recruit only Ugandan residents and will recruit both pregnant women age 16 and above and male or female children.

10.6. Risks and Discomforts

10.6.1. Privacy

Care will be taken to protect the privacy of subjects, as described in this protocol. However, there is a risk that others may inadvertently see patients' medical information, and thus their privacy may be compromised.

10.6.2. Finger Pricks, Heel Sticks, and Venipuncture

Risks of these procedures include pain, transient bleeding and soft-tissue infection.

Risks of Study Medications Risk of Sulfadoxine-Pyrimethamine

Although technically a combination regimen, SP is generally considered a single antimalarial agent, as its success depends on the synergistic action of its two component inhibitors of folate synthesis. SP is currently the standard of care of IPTp throughout sub-Saharan Africa. Adverse reactions listed on the SP package insert are blood dyscrasias (agranulocytosis, aplastic anemia, thrombocytopenia), allergic reactions (erythema multiforme and other dermatological conditions), gastrointestinal reactions (glossitis, stomatitis, nausea, emesis, abdominal pain, hepatitis, diarrhea), central nervous system reactions (headache, peripheral neuritis, convulsions, ataxia, hallucinations), respiratory reactions (pulmonary infiltrates), and miscellaneous reactions (fever, chills, nephrosis); based on widespread experience with the drug, all of these reactions appear to be uncommon or rare with short-term therapeutic use. The best-documented severe adverse effects with SP are cutaneous reactions, primarily noted when SP was used for long-term chemoprophylaxis in non-African populations. Reported rates of serious reactions to SP in the UK, with long-term use for chemoprophylaxis, were 1:2100, with 1:4900 serious dermatological reactions and 1:11,100 deaths.⁷⁴ Estimated rates of toxicity in the US were 1:5000-8000 severe cutaneous reactions and 1:11,000-25,000 deaths.⁷⁵ Clinical experience suggests that risks of severe toxicity are much lower with malaria treatment regimens in Africa.

The WHO currently recommends IPTp with SP in areas with moderate-to-high malaria transmission.²⁸ In a recent systematic review and meta-analysis of 7 trials from sub-Saharan Africa, IPTp with 3 or more doses of SP was associated with a higher birth weight and lower risk of low birth weight compared to 2 doses of SP. In addition there were no differences in the rates of serious adverse events between the two groups.⁷⁶

Risk of Dihydroartemisinin-piperaquine

Risks associated with DP among adults and children. Minyt and colleagues conducted a systematic review of DP efficacy and safety for treatment of malaria using data from 14 clinical trials involving adults and children.⁷⁷ There were 2636 study participants treated with DP in 13 trials in which safety data were reported. Overall, DP was associated with fewer adverse events compared to comparator medications. The most common adverse events were dizziness, nausea and vomiting, though generally the medication was well-tolerated by both adults and children (Table 6). Of note, the only serious adverse events in these 14 studies included 5 deaths (2 adults, 3 children) that were thought unrelated to DP.

Study/site	Nausea	Vomiting	Anorexia	Dizziness	Headache	Diarrhoea	Abdominal pain	Sleep disturbance	Neuropsychiatric adverse events	Cardiovascular dysfunction	Haematological dysfunction	Hepatological dysfunction	Dermatological adverse events	Total no. of evaluated patients
Denis et al. (2002) Cambodia	5 (4.7)	NR	4 (3.8)	5 (4.7)	0 (0)	5 (4.7)	5 (4.7)	NR	NR	NR	NR	NR	1 (0.9)	106
Vilairatana et al. (2002) Thailand	8 (3.4)	0 (0)	NR	11 (4.7)	9 (3.8)	NR	NR	0 (0)	0 (0)	NR	NR	NR	NR	234
ring et al. (2003) China	3 (5)	1 (1.6)	NR	NR	NR	NR	NR	NR	NR	NR	NR	NR	NR	60
Hien et al. (2004) Vietnam	8 (2)	NR	NR	NR	NR	NR	NR	NR	NR	NR	NR	NR	NR	399
Karunajeewa et al. (2004) Cambodia	NR	NR	NR	NR	NR	NR	NR	NR	NR	0 (0)	0 (0)	0 (0)	NR	62
lung et al. (2004) Cambodia	3 (4)	NR	1 (1)	12 (14)	30 (36)	NR	9 (11)	1 (1)	NR	NR	NR	NR	NR	80
Giao et al. (2004) Vietnam	NR	NR	NR	NR	1 (1.2)	NR	NR	NR	NR	NR	NR	NR	1 (1.2)	82
shley et al. (2004) Bangkok, Thailand	11 (9.3)	NR	NR	9 (7.6)	12 (10.2)	NR	NR	NR	NR	NR	NR	NR	NR	118
shley et al. (2004) Mae Sot, Thailand	30 (8.5)	18 (1.7)	NR	51 (14.5)	NR	20 (5.7)	35 (9.9)	20 (7.4)	NR	0 (0)	0 (0)	0 (0)	1 (0.3)	353
shley et al. (2005) Thailand	37 (11.1)	23 (6.9)	NR	37 (11.1)	NR	33 (9.9)	28 (8.4)	42 (12.6)	NR	NR	NR	NR	3 (0.9)	333
angpukdee et al. (2005) Thalland	5 (4.2)	0 (0)	0 (0)	4 (3.3)	4 (3.3)	0 (0)	0 (0)	0 (0)	0 (0)	0 (0)	0 (0)	0 (0)	0 (0)	120
(2006) Myanmar	39 (11.9)	6 (1.8)	10 (8.3)	104 (31.8)	0 (0)	11 (9.2)	3 (0.9)	0 (0)	NR	NR	0 (0)	NR	0 (0)	327
Nayxay et al. (2006) Lao PDR	6 (5.5)	3 (3)	10 (9)	12 (11)	11 (10)	8 (7)	12 (11)	17 (15.5)	0 (0)	NR	NR	NR	0 (0)	110
arema et al. (2006) Rwanda	2 (0.8)	5 (2)	3 (1.2)	1 (0.4)	2 (0.8)	8 (3.2)	6 (2.4)	0 (0)	0 (0)	NR	NR	NR	0 (0)	252

Table 6. Summary of adverse events following treatment with dihydroartemisinin-piperaquine

Data are given as n (%).

More recently Lwin et al conducted a randomized controlled trial of monthly vs. bimonthly DP IPT among 961 adults at high risk of malaria at the Northwest border of Thailand.⁷⁸ Overall, 69% of the participants included in the final analysis reported at least one adverse event. There was no difference in the proportion of those reporting at least one adverse event among participants in the monthly vs. bimonthly vs. placebo arms. There was an increased risk of joint pain among participants randomized to the placebo arm, but otherwise there were no differences noted in adverse events by study arm. There was only one serious adverse event not related to the use of DP (Table 7).

	No. of participants in indicated treatment group who reported adverse event (%) ^a			Incidence rate for indicated group ^b			IRR (95% CI) for DPm and	IRR (95% CI) for DPm and	
Adverse event	DPm	DPalt	Placebo	DPm	DPalt	Placebo	DPalt	placebo	
Dizziness	127 (32.8)	119 (31.2)	49 (25.4)	0.66	0.62	0.69	0.93 (0.72-1.21)	1.05 (0.74-1.47	
Headache	115 (29.7)	108 (28.4)	49 (25.4)	0.60	0.56	0.69	0.93 (0.71-1.23)	1.16 (0.81-1.63	
Soft stool	99 (25.6)	82 (21.5)	29 (15.0)	0.52	0.42	0.41	0.82 (0.61-1.12)	0.80 (0.51-1.22	
Abdominal pain	67 (17.3)	57 (15.0)	28 (14.5)	0.35	0.30	0.40	0.85 (0.58-1.22)	1.14 (0.70-1.79	
Muscle pain	65 (16.8)	63 (16.5)	35 (18.1)	0.34	0.33	0.50	0.96 (0.67-1.38)	1.46 (0.94-2.24	
Fever	47 (12.1)	50 (13.1)	27 (14.0)	0.24	0.26	0.38	1.06 (0.70-1.61)	1.56 (0.94-2.56	
Cough	44 (11.4)	42 (11.9)	17 (8.81)	0.23	0.22	0.24	0.95 (0.61-1.48)	1.05 (0.56-1.88	
Joint pain	40 (10.3)	50 (13.1)	30 (15.5)	0.21	0.26	0.42	1.24 (0.80-1.93)	2.04 (1.23-3.36	
Dry mouth	33 (8.53)	33 (8.66)	11 (5.70)	0.17	0.17	0.16	0.99 (0.60-1.66)	0.91 (0.41-1.84	
Insomnia	34 (8.79)	36 (9.45)	17 (8.81)	0.18	0.19	0.24	1.05 (0.64-1.73)	1.36 (0.71-2.50	
Sleep disturbance.	32 (8.27)	33 (8.66)	14 (7.25)	0.17	0.17	0.20	1.03 (0.61-1.72)	1.19 (0.59-2.29	
Anorexia	24 (6.20)	26 (6.82)	10 (5.18)	0.13	0.13	0.14	1.08 (0.59-1.96)	1.13 (0.48-2.46	
Nausea	22 (5.68)	24 (6.30)	11 (5.70)	0.11	0.12	0.16	1.09 (0.58-2.03)	1.36 (0.60-2.92	
Diarrhea	20 (5.17)	24 (6.30)	5 (2.59)	0.10	0.12	0.07	1.19 (0.63-2.28)	0.68 (0.20-1.87	
Itching	15 (3.88)	8 (2.10)	7 (3.63)	0.08	0.04	0.10	0.53 (0.19-1.33)	1.27 (0.44-3.31	
Vomiting	15 (3.88)	10 (2.62)	3 (1.55)	0.08	0.05	0.04	0.66 (0.27-1.58)	0.54 (0.10-1.92	
Fatigue	15 (3.88)	17 (4.46)	11 (5.70)	0.08	0.09	0.16	1.13 (0.53-2.42)	1.99 (0.83-4.65	
Skin rash	4 (1.03)	4 (1.05)	2 (1.04)	0.02	0.02	0.03	0.99 (0.19-5.34)	1.36 (0.12-9.48	
Palpitation	3 (0.78)	5 (1.31)	3 (1.55)	0.02	0.03	0.04	1.66 (0.32-10.7)	2.72 (0.36-20.3	
Back pain	2 (0.52)	4 (1.05)	2 (1.04)	0.01	0.02	0.03	1.99 (0.29-22.0)	2.72 (0.20-37.5	

Table 7. Frequency, incidence, and risk of the 20 most frequently reported adverse events

" Number of participants who reported an adverse event at least once.

^b Per person-year at risk.

Risks associated the use of DP for IPT in infants. Relevant to this protocol is the PROMOTE Chemoprevention study, an open label randomized clinical trial conducted by our group evaluating the protective efficacy of 3 different chemoprevention regimens against malaria compared to the current standard of care of no chemoprevention. This was the first study to evaluate the safety of DP when used for IPT in infants. DP was shown to be very well-tolerated and associated with a significantly lower rate of all grade 3-4 adverse events, elevated temperature, anemia, and thrombocytopenia compared to the control arm (Table 8).⁷⁹ In addition, 145 ECGs performed 19 study participants randomized to DP documented all QTc intervals to be within normal limits.

Characteristic	Number of events (incidence per PYAR) by treatment arm					
Characteristic	Control	Monthly SP	Daily TS	Monthly DP		
All grade 3-4 adverse events	169 (1·159)	202 (1·415)	135 (0·914)	87 (0·611) ‡		
All serious adverse events	26 (0·178)	52 (0·364)	29 (0·196)	13 (0.091)		
Grade 3-4 adverse events possibly related to study drugs	N/A	8 (0·056)	8 (0·054)	3 (0·021)		
Individual grade 3-4 adverse events*						
Elevated temperature	79 (0·542)	78 (0·546)	58 (0·393)	46 (0·323) ⁺		
Anaemia	56 (0·384)	86 (0.602)	47 (0·318)	24 (0·168) ⁺		
Thrombocytopenia	18 (0·123)	17 (0·119)	9 (0·061)	5 (0·035)α		
Elevated aspartate aminotransferase	7 (0·048)	8 (0·056)	6 (0·041)	3 (0·021)		
Elevated alanine aminotransferase	4 (0·027)	4 (0·028)	4 (0·027)	3 (0·021)		
Neutropenia	3 (0.021)	6 (0·042)	2 (0·014)	1 (0.007)		

Table 8. Comparison of adverse events among children between 6-24 months of age

PYAR = person-years at risk.

SP = sulfadoxine-pyrimethamine. TS = trimethoprim-sulfamethoxazole. DP = dihydroartemisinin-piperaquine.

* Only includes those with at least 5 total events.

 $^{\alpha}$ p-value < 0.05 compared to control group; $^{+}$ p-value < 0.01 compared to control group; $^{+}$ p-value < 0.001 compared to control group.

Risks associated with DP during pregnancy. While data are limited, preclinical animal studies ⁸⁰⁻ ⁸² and clinical studies involving pregnant women ^{22,23} have not demonstrated significant safety concerns with the use of DP. In a recent study from Kenya, serious adverse events were less frequent in women randomized to IPTp with DP compared to women randomized to IPTp with SP.²⁵ In a recent study from our group comparing IPTp with 3 dose SP vs. 3 dose DP vs. monthly DP in Tororo Uganda, study drugs were well tolerated and there were no significant differences in the risk of adverse events.²⁶ Vomiting occurred < 0.2% of the time after administration of study drugs with no differences between study arms (Table 9). There were no significant differences in the incidence of any adverse events apart from dysphagia, which was higher in the monthly DP arm compared to the 3 dose DP arm. All episodes of dysphagia were mild in severity and we are not aware of any previous reports of DP being associated with dysphagia. Only one grade 3-4 adverse event was possibly related to study drugs; an episode of anemia which occurred both after the 1st and 2nd doses of monthly DP (study drug was subsequently withheld after the 2nd dose)(Table 9). Among 42 women who underwent ECG measurements at 28 weeks gestational age, all pre- and post-dosing QTc intervals were within normal limits (< 450 msec) and no clinical adverse events consistent with cardiotoxicity occurred during the course of the study. Median change in QTc intervals was greater in the 3 dose DP (20 msec) and monthly DP (30 msec) arms compared to the 3 dose SP arm (5 msec), but these differences were not statistically significant.

Outcome		Treatment arm	
Outcome	3 dose SP	3 dose DP	Monthly DP
Prevalence measures	no./total no. (%)	no./total no. (%)	no./total no. (%)
Vomiting following administration of study drugs			
Observed after administration of 1 st dose in clinic	2/617 (0.32)	0/542 (0)	1/594 (0.17)
Reported after administration of 2 nd or 3 rd dose at home	2/1222 (0.16)	0/1067 (0)	5/1180 (0.42)
Incidence measures	Events ^a	Events ^a	Events ^a
Individual adverse events of any severity ^b			
Abdominal pain	172 (3.14)	122 (2.52)	132 (2.47)
Cough	94 (1.72)	71 (1.47)	77 (1.44)
Headache	90 (1.64)	70 (1.45)	78 (1.46)
Chills	21 (0.38)	14 (0.29)	12 (0.22)
Diarrhea	12 (0.22)	10 (0.21)	13 (0.24)
Malaise	16 (0.29)	9 (0.19)	8 (0.15)
Dysphagia	9 (0.16)	2 (0.04)	14 (0.26) ^c
Vomiting	8 (0.15)	8 (0.17)	8 (0.15)
Nausea	2 (0.04)	4 (0.08)	2 (0.04)
Urinary tract infection	3 (0.05)	2 (0.04)	2 (0.04)
Anorexia	2 (0.04)	0 (0)	4 (0.07)
Individual grade 3-4 adverse events			
Anemia	12 (0.22)	4 (0.08)	6 (0.11)
Congenital anomaly	2 (0.04)	4 (0.08)	0 (0)
Stillbirth	1 (0.02)	1 (0.02)	1 (0.02)
Thrombocytopenia	2 (0.04)	0 (0)	0 (0)
Threatened abortion	1 (0.02)	0 (0)	0 (0)
Retained products of conception	0 (0)	1 (0.02)	0 (0)
Preeclampsia	0 (0)	0 (0)	1 (0.02)
Hypotension	0 (0)	0 (0)	1 (0.02)
Pyelonephritis	0 (0)	1 (0.02)	0 (0)
Respiratory distress	0 (0)	1 (0.02)	0 (0)
All grade 3-4 adverse events	18 (0.33)	12 (0.25)	9 (0.17)
Grade 3-4 adverse events possibly related to study drugs	0 (0)	0 (0)	1 (0.02)
All serious adverse events	6 (0.11)	9 (0.19)	4 (0.07)

Table 9. Measures of safety and tolerability from recent IPTp study conducted in Tororo, Uganda

^a Number of events (incidence per person year at risk)

^b Includes only those categories with at least five total events

^cP=0.02 comparing monthly DP with 3 dose DP

